10.1.7	Publication and Data Sharing Policy	20
10.1.8	Conflict of Interest Policy.....	20
10.2	Abbreviations.....	21
11	REFERENCES.....	22

STATEMENT OF COMPLIANCE

The protocol, informed consent form(s), recruitment materials, and all participant materials will be submitted to the IRB for review and approval. Approval of both the protocol and the consent form must be obtained before any participant is enrolled. Any amendment to the protocol will require review and approval by the IRB before the changes are implemented to the study. All changes to the consent form will be IRB approved; a determination will be made regarding whether a new consent needs to be obtained from participants who provided consent, using a previously approved consent form.

1 PROTOCOL SUMMARY

1.1 SYNOPSIS

Title:	Optimizing fluoride retention in the mouth of older adults with distinct salivary flow rates
Study Description:	This study will assess the effect of an improved fluoride mouth rinse (combined with a calcium prerinse) on enhancing the retention of fluoride in the mouth of older adults with saliva flow ranging from normal to hyposalivation. The study hypothesis is that the calcium prerinse will increase the retention of fluoride in the mouth of older adults, when compared with the fluoride rinse alone.
Objectives:	
Primary Objective: Determine the benefit of using a calcium mouth rinse, before a fluoride mouth rinse, to enhance fluoride retention in the mouth of individuals with hyposalivation.
 
Secondary Objectives: To determine the role of hyposalivation on the retention of fluoride in the mouth after a fluoride rinse.

Endpoints:	
Primary Endpoint: Fluoride concentration in dental plaque (biofilm) up to 2 h after a mouth rinse
 
Secondary Endpoints: Fluoride concentration in saliva up to 2 h after a mouth rinse; Calcium concentration in dental plaque and saliva up to 2 h after a mouth rinse

Study Population:	Twenty individuals, with 65 years of age or more, from both genders, with good general health, independent, with good oral health, from the Ann Arbor, MI area. At least 10 individuals should have signs of hyposalivation (dry mouth).
Phase:	1
Description of Sites/Facilities Enrolling Participants:	Participants will be recruited among patients from the School of Dentistry, University of Michigan, in Ann Arbor, MI.
Description of Study Intervention:	The study will have 2 interventions (crossover design): a. a sodium fluoride mouth rinse at an over-the-counter concentration of 0.05% (226 ppm of fluoride), used for 1 min; b. a calcium mouth rinse (calcium lactate at a

[figure not shown]
concentration of 150 mM) used for 1 min, followed by the sodium fluoride mouth rinse described in a.

Study Duration: 36 months

Participant Duration: 1 month

1.2 SCHEMA

Flow diagram of the study

1.3 SCHEDULE OF ACTIVITIES (SOA)

Procedures	Baseline, Visit 1 Day 0	Study Visit 2 Day 7 (+1 month)	Study Visit 3 Day 14 (+1 month)
Informed consent	X		
Demographics	X		
Medical history	X		
Intra-oral exam	X		
Saliva flow rate assessment	X		
Randomization	X		
Administer study intervention		X	X
Saliva samples collection		X	X
Dental biofilm samples collection		X	X
Adverse events reporting		X	X

2 INTRODUCTION

2.1 STUDY RATIONALE

Saliva plays a major role in maintaining oral health. A reduction in saliva flow (hyposalivation) drastically increases the risk for oral diseases, including cavities. Hyposalivation (dry mouth) is a special concern for older individuals: about 80% of American people over 65 years of age have at least one chronic condition and 68% have at least two [National Council on Aging, 2015]. Many of the medications used to control these conditions cause hyposalivation [Wolff et al., 2017]. Also, with aging there is a natural exposure of the teeth roots to the oral cavity, and these are more susceptible to cavities due to the higher solubility of their cementum/dentin when compared with the enamel covering the teeth crowns. Therefore, maintaining oral health in older individuals with dry mouth is challenging; the resulting pain, poor nutrition and impaired social functions add to the overall reduction in quality of life in these older adults already suffering from dry mouth.

Fluoride has been successfully used to maintain oral health, especially in dry mouth patients. Yet, the kinetics of fluoride in the mouth of older adults, including those with hyposalivation, is poorly understood. Although they need to use fluoride in higher concentrations, such as prescription toothpastes containing 5,000 ppm of fluoride (F), the extent of the effectiveness of using higher fluoride concentrations in hyposalivation patients has scarcely been explored. Even in individuals with normal salivary flow, the use of a 5,000 ppm F rinse does not result in the expected increased retention of fluoride in the mouth [Staub Larsen et al., 2018], suggesting that there is a limit for increasing intraoral fluoride concentration from oral hygiene products when aiming at increasing their retention. This may be due to the limited supply of positively charged cations, such as calcium, to which fluoride could be bound, to be retained for longer periods in the mouth [Vogel 2011]. Alternative approaches aiming to optimize the fluoride retention by previously supplying a calcium source have been developed [Vogel et al., 2006a, 2006b, 2008a, 2008b], but never tested in hyposalivation patients. For instance, the use of a calcium rinse before a fluoride rinse (Ca→F) successfully enhances fluoride retention in the mouth [Souza et al., 2016], under normal salivary flow conditions. This approach could be particularly helpful for hyposalivation patients, by also providing a supply of calcium ions, which are limited due to the low saliva production.

In the present trial, the effect of salivary flow rate (from normal to hyposalivation) on the retention of fluoride in the mouth of older adults after a fluoride rinse will be studied. We hypothesize that although a reduction in salivary flow reduces the rate of clearance of fluoride from the mouth, the lower availability of calcium ions due to the lack of saliva also reduces fluoride retention. Also, the effect using a calcium rinse before the fluoride rinse to increase fluoride retention in the mouth will be tested in older individuals with a range of salivary flow rates. We hypothesize that the increased retention of fluoride observed after a calcium prerinse will be enhanced in individuals with low saliva flow.

2.2 BACKGROUND

Dry mouth is a serious and prevalent problem in older adults [Furness et al., 2011] and is associated with increased risk for oral diseases, such as caries [Navazesh, 2012]. The lack of saliva reduces the clearance of cariogenic sugars and acids from the dental biofilm, impairs the action of salivary buffering agents and reduces the supply of calcium and phosphate ions, which are natural remineralizing agents [Edgar et al., 2012]. Based on limited evidence, higher fluoride concentration products are usually recommended for older adults with hyposalivation [Zero et al., 2016].

Nevertheless, previous studies have shown that a calcium (Ca) prerinse can boost the retention of F in the mouth [Vogel et al., 2006a; 2006b; 2008a; 2008b; Souza et al., 2016], enhancing its effect. Although the effect of the Ca prerinse on F availability in hyposalivation patients has never been studied, preliminary data give support to the enhanced effect expected for this procedure. Using an in situ model, it was shown that a Ca prerinse used before a F rinse for 14 days increased ~22 and 4-fold the F and Ca concentrations in dental biofilm, respectively [Souza et al., 2016]. This corroborates the hypothesis that the retention of F in the mouth can be enhanced, without the need to increase the F concentration in them. The increased F and Ca retention may be particularly useful for hyposalivation patients.

In the current project we aim to assess the effect of this approach in maintaining increased and sustained levels of Ca and F in the oral fluids of patients with a range of salivary flow rates, varying from normal to hyposalivation. There are no known risks associated with the use of these rinses.

2.3 RISK/BENEFIT ASSESSMENT

2.3.1 KNOWN POTENTIAL RISKS

No more than minimal risks are expected to participants enrolled in this trial. The discomforts/risks are listed below:

Immediate discomforts/risks:

1. Discomfort related to refraining from tooth brushing from the previous night until the morning of rinses and sampling collection. This is expected to be a common discomfort (incidence > 25%). The subject may feel malodor in the morning of the test due to the suspension of oral hygiene. After the sampling is completed, the subject will receive a professional cleaning or supervised toothbrushing to remove remnants of dental plaque.
2. Discomfort related to collecting saliva samples. This is expected to be a likely discomfort (10-25%), as some individuals do not feel comfortable in spitting saliva into a tube. This discomfort will be minimized by maintaining the subject in a private dental chair, with only the trained study staff offering instructions on the procedure.

3. Discomfort related to rinsing with unflavored rinses. This is expected to be a likely discomfort (10-25%), as the rinses will be prepared from reagent grade chemicals, with no flavoring agents.
4. Discomfort related to refraining from eating or drinking for up to 2 hours during the collection of samples. This is expected to be a likely discomfort (10-25%). This may be more disturbing for individuals with reduced saliva flow, if they are used to sip water constantly. If the subject (especially those with dry mouth) feel the need of drink water during the two-hour period after the rinse, he/she will be allowed to do so, and notes taken as protocol deviation in order to later assess their effect on the study outcomes.

Long-range risks:

1. Loss of confidentiality of the study records. This risk is expected to be rare. To minimize the risk of confidentiality breach, data will be stored in password-protected electronic files or locked storage cabinets accessible only to the study personnel. Standards for data collection, management and analysis will be followed.

2.3.2 KNOWN POTENTIAL BENEFITS

The subjects will receive oral hygiene and care instructions provided by the study personnel. Also, in case they have hyposalivation, they will be informed about this, because this condition is not necessarily perceived by the patients and it increases the risk for oral diseases.

The subjects may also benefit from the understanding of the study objectives, making them better aware of the importance taking care of their oral health.

2.3.3 ASSESSMENT OF POTENTIAL RISKS AND BENEFITS

The risks/discomfort associated with this study are no more than minimal. The subjects will be informed about them and should agree to participate before being enrolled. They will benefit from learning about their oral health and good oral hygiene practices.

By investigating an easy and inexpensive procedure to enhance the effect of fluoride, this research will help develop a more effective and cost-benefit way for fluoride use, without the need to increase the fluoride concentration. This potential benefit, especially for vulnerable groups like elders with hyposalivation, outweigh the minimal risks associated with the trial. No risks associated with the use of the mouth rinses are expected.

3 OBJECTIVES AND ENDPOINTS

OBJECTIVES	ENDPOINTS	JUSTIFICATION FOR ENDPOINTS
Primary		
Determine the benefit of using a calcium rinse, before a fluoride rinse, to enhance fluoride retention in dental biofilm of individuals with hyposalivation.	Fluoride concentration in dental biofilm (fluid and solid phase) up to 2 h after rinsing with fluoride.	Dental biofilm can take up fluoride and release it for prolonged periods of time, like the hours in between oral hygiene procedures.
Secondary		

OBJECTIVES	ENDPOINTS	JUSTIFICATION FOR ENDPOINTS

Determine the benefit of using a calcium rinse, before a fluoride rinse, to enhance fluoride retention in saliva of individuals with hyposalivation.
	
 1. Fluoride concentration in saliva up to 2 h after rinsing with fluoride. 2. Calcium concentration in dental biofilm (fluid and solid phase) up to 2 h after rinsing with fluoride. 3. Calcium concentration in saliva up to 2 h after rinsing with fluoride. 	
 1. Salivary fluoride can be considered as a surrogate measure of fluoride availability in the mouth, because from saliva fluoride from rinses gets to dental biofilm. 2. Since a calcium rinse will be used in one of the treatments in this study, determination of calcium concentration in dental biofilm will be made to identify potential sources of fluoride retention (e.g. fluoride bound to calcium ions, calcium fluoride precipitation). 3. Salivary calcium can be considered as a surrogate measure of calcium availability in the mouth; since a calcium rinse will be used in one of the study treatments, salivary calcium will be determined.
Tertiary/Exploratory		

Determine the role of hyposalivation on the retention of fluoride in the mouth after a fluoride rinse
	
 1. Correlation between salivary flow rate and fluoride concentration in dental biofilm up to 2 h after a rinse. 2. Correlation between salivary flow rate and fluoride concentration in saliva up to 2 h after a rinse. 	
The correlation between salivary flow rate and fluoride in dental biofilm and saliva will be investigated to estimate how the flow rate affect these variables.

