9 STATISTICAL CONSIDERATIONS

9.1 Statistical Hypotheses

- **Primary Efficacy Endpoint:**
- Fluoride concentration in dental biofilm
 - Null hypothesis: A fluoride rinse preceded by a calcium rinse is not superior than a fluoride-only rinse in enhancing fluoride concentration in dental biofilm (fluid and solid phases) up to 2 h after mouth rinsing.
 - Alternative hypothesis: A fluoride rinse preceded by a calcium rinse is superior than a fluoride-only rinse in enhancing fluoride concentration in dental biofilm (fluid and solid phases) up to 2 h after mouth rinsing.
- **Secondary Efficacy Endpoints:**
- Fluoride concentration in saliva
 - Null hypothesis: A fluoride rinse preceded by a calcium rinse is not superior than a fluoride-only rinse in enhancing fluoride concentrations in saliva up to 2 h after mouth rinsing.
 - Alternative hypothesis: A fluoride rinse preceded by a calcium rinse is superior than a fluoride-only rinse in enhancing fluoride concentrations in saliva (fluid and solid phases) up to 2 h after mouth rinsing.
- Calcium concentration in dental biofilm
 - Null hypothesis: A fluoride rinse preceded by a calcium rinse is not superior than a fluoride-only rinse in enhancing calcium concentration in dental biofilm (fluid and solid phases) up to 2 h after mouth rinsing.

- Alternative hypothesis: A fluoride rinse preceded by a calcium rinse is superior than a fluoride-only rinse in enhancing calcium concentration in dental biofilm (fluid and solid phases) up to 2 h after mouth rinsing.
- Calcium concentration in saliva
 - Null hypothesis: A fluoride rinse preceded by a calcium rinse is not superior than a fluoride-only rinse in enhancing calcium concentration in saliva up to 2 h after mouth rinsing.
 - Alternative hypothesis: A fluoride rinse preceded by a calcium rinse is superior than a fluoride-only rinse in enhancing calcium concentration in saliva up to 2 h after mouth rinsing.
- Tertiary/exploratory Endpoints:
- Correlation between salivary flow rate and fluoride concentration in dental biofilm
 - Null hypothesis: There is no correlation ($\beta = 0$) between salivary flow rate and fluoride concentration in dental biofilm after rinsing with a fluoride mouth rinse.
 - Alternative hypothesis: There is a correlation ($\beta \neq 0$) between salivary flow rate and fluoride concentration in dental biofilm after rinsing with a fluoride mouth rinse.
- Correlation between salivary flow rate and fluoride concentration in saliva

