9.3 POPULATIONS FOR ANALYSES

For the primary and secondary outcomes, only participants completing the whole study will provide data for the analyses (per-protocol analysis).

For the tertiary outcomes, a modified intention-to-treat analysis will be used; all volunteers completing the fluoride-only mouth rinse treatment will provide data for the correlation analyses, even if they did not complete the other study treatment.

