9.4.2 ANALYSIS OF THE PRIMARY EFFICACY ENDPOINT(S)

Fluoride concentration in dental biofilm (primary efficacy endpoint) will be determined from the samples collected at baseline and 15 min, 60 min and 120 min (± 5 min) after rinsing with the assigned mouth rinse(s). The concentration at each individual timepoint will be compared between the two intervention groups. Also, the area under the curve of fluoride concentration in dental biofilm versus time will be calculated. This single measurement of fluoride bioavailability overtime after the mouth rinse(s) will be compared between the two intervention groups.

Each set of data will be checked for normality of errors. If the data is not normal, it will be log-transformed. An analysis of variance will be conducted, considering as factors the participant (experimental block) and the treatment. The use of the participant as a source of variation aims solely to reduce unknown variability in the error. An alpha level of 5% will be used to determine significant differences between the two groups.

In case data were log-transformed to fit the statistical analysis, their geometric means and confidence intervals (calculated from the log-transformed data) will be presented.

If data is missing from one of the intervention groups, the rest of the participant data (from the other intervention) will be excluded from the analysis.

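### The primary objective and section 3's saliva objective concern people with hyposalivation, but no planned analysis estimates the calcium prerinse effect in them

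*Combined protocol and SAP*

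**What the plan says.** **Objectives.** Section 3 gives the primary objective as "Determine the benefit of using a calcium rinse, before a fluoride rinse, to enhance fluoride retention in dental biofilm of individuals with hyposalivation". Its secondary objective has the same form for saliva: "to enhance fluoride retention in saliva of individuals with hyposalivation". The synopsis (1.1) sets the primary objective as the benefit of the calcium rinse "to enhance fluoride retention in the mouth of individuals with hyposalivation".

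**Rationale.** Section 2.1 expects the gain from the prerinse to be larger when saliva flow is low. It also says the prerinse will be studied across a range of flow rates.

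**Enrolment.** Section 8.1, item 3, caps normal-flow participants at 10 of 20. It expects low flow in more than half and would allow all 20 to have hyposalivation.

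**Analysis.** The primary alternative hypothesis in 9.1 names no flow group: "A fluoride rinse preceded by a calcium rinse is superior than a fluoride-only rinse in enhancing fluoride concentration in dental biofilm". Section 9.3 takes every participant who completes the study for the primary and secondary outcomes. The ANOVA in 9.4.2, repeated in 9.4.3, is run "considering as factors the participant (experimental block) and the treatment". Flow rate appears only in the tertiary analysis, whose biofilm hypothesis concerns the correlation between "salivary flow rate and fluoride concentration in dental biofilm after rinsing with a fluoride mouth rinse". For its data, 9.3 says "all volunteers completing the fluoride-only mouth rinse treatment will provide data for the correlation analyses".

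**The concern.** The primary objective and the section 3 saliva objective ask what the prerinse does in people with hyposalivation. The planned contrast averages over everyone who completes, and half of them could have normal flow. Nothing in section 9 estimates the effect in the named group or looks at whether the effect changes with flow, as section 2.1 predicts.

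Sections 2.1 and 2.2 say the approach has never been tested in hyposalivation patients, so this is the new information the trial could give. Followed exactly, the plan could end with a pooled ratio that understates the gain at low flow if section 2.1 is right. It could also lead to a pooled result being reported as benefit in hyposalivation when no estimate was made there.

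**Working it through.** **1. Is the named population analysed anywhere?**

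| Planned analysis | Participants | Prerinse contrast? | Uses flow? |
|---|---|---|---|
| ANOVA, 9.4.2 | all completers | yes | no |
| ANOVA, 9.4.3 | all completers | yes | no |
| Regression, 9.4.1 (hypotheses 9.1, data 9.3) | completers of the fluoride-only rinse | no | yes |

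No row has both a prerinse contrast and flow. Using the participant as a block removes differences in fluoride level between people, including those due to flow. It does not estimate the prerinse effect at low flow.

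**2. The plan's own figures.** Section 9.2 gives 15 participants for 80% power at 5%, raised to 20 for 30% attrition. The 15 cannot be reproduced because 9.2 gives no effect, SD, scale or sidedness. The 20 matches 15 × 1.3 = 19.5. With 30% attrition, the guaranteed 10 with hyposalivation become 10 × 0.7 = 7.

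**3. What the pooled mean estimates.** Let the log-ratio effect be δ in hyposalivation and, by assumption, δ/2 at normal flow.
- 10+10: (10δ + 10δ/2)/20 = 0.75δ.
- 13+7, an illustration of low flow in more than half: (13δ + 7δ/2)/20 = 0.825δ.

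**4. Power of a hyposalivation-only paired test, one-sided 5%.** Power is P(T > t(0.95, n−1)), with T noncentral t on n−1 df and noncentrality dz·√n. Here dz is the mean within-person log ratio divided by its SD.

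*Reading A: n=15 gives 80% power in a paired test.* Solving for dz gives 0.675 if that calculation was one-sided and 0.778 if two-sided.
- n=10: 63% to 73%.
- n=7: 48% to 57%.

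*Reading B: the roughly 22-fold rise in biofilm fluoride in 2.2 applies.* It comes from the study that 9.2 used for the sample size, after 14 days of use in an in situ model, with no SD given. ln 22 = 3.09. With an assumed log-ratio SD of 1 to 2, dz is 3.09/1 = 3.09 down to 3.09/2 = 1.55.
- n=7, at the lower dz: 97%.
- n=10, at the lower dz: above 99%.

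The readings agree only if the log-ratio SD is 3.09/0.778 = 4.0 to 3.09/0.675 = 4.6, a 53- to 97-fold spread per SD.

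**5. Width of the interval.** The 95% half-width is t(0.975, n−1)·SD/√n. At n=10 this is 2.262/√10 = 0.715 SD. For a log SD of 1 to 2 it is 0.715 to 1.431, or a factor of 2.0 to 4.2 either way.

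**6. Sequence balance within the hyposalivation group.** Section 6.3 allocates 10 participants to each order, without stratifying by flow. With 10 hyposalivation participants among 20, the chance of a 7:3 or worse split is 2 × [C(10,7)² + C(10,8)² + C(10,9)² + C(10,10)²]/C(20,10) = 2 × (14,400 + 2,025 + 100 + 1)/184,756 = 0.179. At 7:3, an unadjusted mean within-person difference carries (7 − 3)/10 = 0.4 of any period effect.

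**The case against.** The strongest reply is that most of the plan targets the whole flow range: the title, the synopsis hypothesis, 2.1, 2.2, 4.1 and 9.1 all speak of older adults generally. On that view the objectives are loosely worded, and broadening them would remove the mismatch. This stands in part. Rewording is a legitimate route, and the effect-modification sentence in 2.1 is rationale that neither section 3 nor 9.1 takes up. But the primary objective names hyposalivation in both places where it is stated.

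It can also be said that all 20 may have hyposalivation. That is true, and if nearly all do, the gap closes. The plan does not require it.

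A reader might go further and infer three things that the documents do not support.
- *That the pooled ANOVA is wrong.* It is a valid test of the hypothesis in 4.1 and 9.1.
- *That a hyposalivation estimate must be imprecise, or a flow analysis uninformative.* That holds only under reading A. The fold increase in 2.2 points the other way, and no SD is given to decide between them.
- *That every secondary objective is affected.* The synopsis secondary objective concerns the role of hyposalivation after a fluoride rinse, not the prerinse. Only section 3's secondary objective belongs here.

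A pooled success with no effect in hyposalivation is conceivable, but 2.1 and 2.2 argue the reverse, so the point does not rest on it.

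**Conclusion.** The concern holds and should be fixed. The primary objective (1.1 and section 3) and the saliva objective (section 3) have no matching analysis unless nearly all who enrol have hyposalivation. This follows from the text and needs no assumed number.

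The size is conditional. The 75% and 82% figures assume a normal-flow effect half as large. Power for the named group runs from 48-57% (n=7, reading A) to at least 97% (n=7, reading B), depending on an SD the documents do not give. This range supports asking for an estimate with an interval. It does not support declaring the trial too small, or large enough, for that group.

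**What to change.** 1. Keep the pooled ANOVA.
2. Add to 9.4.2 and 9.4.3 the geometric mean ratio of fluoride AUC (calcium then fluoride versus fluoride only) with 95% CI in hyposalivation participants and, for context, in normal-flow participants. Label it estimation only.
   - Use the flow cut-offs in 8.1, item 2, and state whether meeting either one suffices.
   - Report biofilm fluid and solid fluoride, and one saliva measure named in advance, since 8.1, item 5, analyses saliva both before and after centrifugation.
   - Adjust for period, because randomisation is not stratified by flow.
3. Optionally, add a supportive regression of the within-person log AUC ratio on one prespecified continuous flow measure.
4. Reconcile the primary objective (1.1 and section 3) and section 3's secondary objective with 9.1, so that a pooled result alone is not reported as benefit in hyposalivation. Whether to broaden the objectives or answer them through the hyposalivation estimate is the sponsor's choice.

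**Cost.** Wording and a little more analysis. Flow is measured in everyone at visit 1 and the AUCs are already planned, so enrolment, visits and the primary test do not change. The subgroup is small and its precision may be low. The period term costs one degree of freedom, so intervals will be slightly wider than those shown above.
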